9.4.4. Early withdrawal visit

- Not applicable as will continue to be followed up as per standard NHS/T2T care

9.4.5. Safety follow-up visit

- Not applicable as will continue to be followed up as per standard NHS/T2T care

9.4.6. Unscheduled visits

- For patients who do not tolerate their medication or are flaring outside of the study schedule.
- Will be recorded in the medical notes and in the CRF.
- If side effects related to IMP to be recorded as an adverse event
- Any changes to treatment to be documented

- **General**

- Assess compliance with treatment
- Clinical observations will be performed as per standard care (not required as a research parameter)
- Medication, allergy and co-morbidity check

- **Clinical assessment data**

- Physical examination if clinically indicated

- **Laboratory tests**

- Routine haematology and biochemistry suitable for diagnostic investigation & therapeutic DMARD monitoring FBC, U&E, LFT & eGFR ml/min/1.73 m²
- Urinalysis/pregnancy test if clinically indicated

- **Adverse event recording**

If the reason for the visit is a flare, the following assessments will also be done:

- **Clinical assessment data**

- Joint examination performed by an independent assessor:
 - Tender joint count (28)
 - Swollen joint count (28)
- Disease activity score (DAS28)
- Clinical disease activity index (CDAI)
- Simplified disease activity index (SDAI)
- Early morning stiffness (mins)

- **Laboratory tests**

- *Naïve CD4+ T-cells*
- ESR (mm/h) & CRP (mg/L)

- **Patient reported outcomes**

- Visual analogue scores of pain/disease activity/general health
- Physician assessment of general health
- HAQ-DI

- ***Imaging***

- o Power Doppler Ultrasound (PDUS) of standard set of 26 and 6 tendons joints for grey-scale (GS), power Doppler (PD), erosions (E) and osteophytes (O) and tenosynovitis (TSV)
- Management of DMARD treatment/administration of corticosteroid treatment will be at the discretion of the treating study physician

10. PHARMACOVIGILANCE

10.1 Defining adverse events

An **adverse event** (AE) is any untoward medical occurrence in a patient during or following administration of an investigational product and which does not necessarily have a causal relationship with treatment. An AE can therefore be any unfavourable and unintended sign (including an abnormal laboratory finding), symptom, or disease temporarily associated with the use of the trial drugs, whether or not considered related to the trial drugs.

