1.2 Investigational medicinal product (IMP)

Within the trial, the following is classed as an Investigational Medicinal Product (IMP):

- ***Benepali®:***

- Etanercept biosimilar
- Administered subcutaneously (sc) 50mg/week
- In combination with MTX is indicated for the treatment of moderate to severe active RA in adults when the response to disease-modifying anti-rheumatic drugs, including MTX (unless contraindicated), has been inadequate
- Can be given as monotherapy in case of intolerance to MTX or when continued treatment with MTX is inappropriate
- Also indicated in the treatment of severe, active and progressive RA in adults not previously treated with MTX
- Has been shown to reduce the rate of progression of joint damage as measured by X-ray and to improve physical function (alone or in combination with MTX)[17]

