4.2. Efficacy variables

- Tender joint count (range 0-28)
- Swollen joint count (range 0-28)
- Erythrocyte sedimentation rate (mm/hr)
- C-reactive protein (mg/L)
- DAS28 disease activity (derived; range 0-10)
- CDAI disease activity (derived; range 0-76)
- SDAI disease activity (derived; range 0-86)
- ACR/Boolean remission status (derived; yes/no)
- Physician global assessment VAS (mm; range 0-100)
- Early morning stiffness (EMS) (mins; range 0-720)
- Patient general health VAS (mm; range 0-100)
- Patient assessment of disease activity VAS (mm; range 0-100)
- Patient assessment of pain VAS (mm; range 0-100)

- Health Assessment Questionnaire Disability Index (HAQ-DI) (range 0-3)
- Number of joints scoring PD>0 (range 0-13 bilaterally), and tendons (range 0-5 bilaterally)
- Number of joints scoring GS>1 (range 0-13 bilaterally), and tendons (range 0-5 bilaterally)
- Naïve T-cell frequency (%)

4.3. *Exploratory biomarkers*

Serum and plasma samples collected at baseline and at Week 24 will also be stored (for future evaluation of disease categorization, auto-antibodies, inflammatory, immunological and vascular biomarkers and products of synovial, cartilage and bone turnover in this and future studies (subject to ethical review of such studies)).

A maximum of 40ml of blood will be drawn at each relevant visit. This will be collected, processed and stored in accordance with local practice.

4.4. *Safety variables*

- Number of patients experiencing SAEs and AEs. [L]
[SEP]
- Any clinically significant worsening of a pre-existing condition. [L]
[SEP]
- An AE occurring from overdose of an IMP, whether accidental or intentional. [L]
[SEP]
- An AE occurring from abuse (e.g. use for non-clinical reasons) of an IMP
- An AE that has been associated with the discontinuation of the use of an IMP

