7. STUDY TREATMENTS

7.1. General information on the products (trial drugs) to be used

Within the trial, the following is classed as an Investigational Medicinal Products (IMP):

- **Benepali®:** In combination with MTX is indicated for the treatment of moderate to severe active RA in adults when the response to disease-modifying anti-rheumatic drugs, including MTX (unless contraindicated), has been inadequate.
 - Can be given as monotherapy in case of intolerance to MTX or when continued treatment with MTX is inappropriate.
 - Also indicated in the treatment of severe, active and progressive RA in adults not previously treated with MTX.
 - Has been shown to reduce the rate of progression of joint damage as measured by X-ray and to improve physical function (alone or in combination with MTX)[17].

MTX in a non-IMP as it is not being used in this study outside its licensed use. It is used as a first-line therapy for RA. Similarly, hydroxychloroquine (HCQ), sulfasalazine (SSZ) and folic acid (FA) are non-IMPs.

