10.5. Recording and reporting of AEs

10.5.1. Recording and reporting of all AEs

Determination of AEs should be based on the signs or symptoms detected during the physical examination and on clinical evaluation of the subject, and should be assessed and recorded at every visit. Signs and symptoms must be recorded using standard medical terminology. Subjects considered incapable of giving consent would not be considered for this study.

AEs and SAEs will be collected from the signing of the informed consent form until the last follow up visit. The Investigator must instruct the subject to report AEs and SAEs during this time period.

During the time period specified above, the Investigator will:

- Record all AEs and SAEs on source documents.
- Record all AEs and SAEs in the CRF for subjects who are not screen failures.

The Investigator must follow up on all AEs and SAEs until the events have subsided, returned to baseline, or, in case of permanent impairment, until the condition has stabilized, within the duration of the trial for each participant. There will be no follow up of AE's past the last follow up visit for each participant.

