#### Safety

The number of patients experiencing SAEs and AEs, any clinically significant worsening of a pre-existing condition, an AE occurring from overdose (accidental or intentional) of an IMP, an AE

occurring from abuse of an IMP or an AE associated with the discontinuation of the use of an IMP will be recorded.

Biochemistry and haemotology parameters will be collected at all visits.

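### AE wording is inconsistent about the IMP, and the overdose, abuse and AE-related discontinuation variables name only an IMP, so they are empty by construction in Arms A and B

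*Protocol*

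**What the plan says.** **Which drug is the IMP.** Protocol 1.2 and 7.1 class only Benepali as an IMP. On methotrexate, 7.1 says "MTX in a non-IMP as it is not being used in this study outside its licensed use", and it gives hydroxychloroquine, sulfasalazine and folic acid the same status. Protocol 5.1 assigns Benepali to Arm C alone.

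**Wording tied to the IMP.** Protocol 10.1 begins by saying that an AE "is any untoward medical occurrence in a patient during or following administration of an investigational product". At unscheduled visits, which serve patients who are flaring or cannot tolerate their medication, 9.4.6 has the bullet "If side effects related to IMP to be recorded as an adverse event". Protocol 4.4 includes among the safety variables "An AE that has been associated with the discontinuation of the use of an IMP", next to AEs from overdose and from abuse of an IMP. SAP 7.3 repeats the list and ends with "an AE associated with the discontinuation of the use of an IMP will be recorded".

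**Wording that covers every arm.** The second sentence of 10.1 reaches any unfavourable sign, symptom or disease "associated with the use of the trial drugs, whether or not considered related to the trial drugs". Protocol 10.5.1 states that "AEs and SAEs will be collected from the signing of the informed consent form until the last follow up visit" and requires CRF entry for every subject who is not a screen failure. The safety set (Protocol 12.4, SAP 11.2) is defined by study treatment, and SAP 11.7.1 reports serious and non-serious AEs for each trial group.

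**The concern.** Two different bases for safety recording run through the same documents: exposure to the IMP, and participation in the trial. Arms A and B are never assigned the IMP, so any item resting on the first basis has no possible events there.

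For the AE definition, the risk is inconsistent reading by the people completing the CRF. For the three IMP-specific variables, the asymmetry is in the wording itself. In the randomised B versus C comparison they can be non-zero only in Arm C. In all three arms, a patient who stops a conventional DMARD because of an adverse event is not counted by the only variable that links an AE to stopping treatment.

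**Working it through.** No power or error-rate calculation applies. The check compares the texts and works out one proportion.

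**Step 1. Does the AE definition exclude Arms A and B?**

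| Place | Basis | Covers Arms A and B? |
|---|---|---|
| Protocol 10.1, first sentence | Investigational product | Not as written |
| Protocol 10.1, second sentence | Trial drugs, related or not | Yes, if the term includes methotrexate |
| Protocol 9.4.6, side-effect bullet | IMP | No |
| Protocol 9.4.6, separate AE-recording line | None stated | Yes |
| Protocol 9.1 schedule (weeks 4, 12, 24, unscheduled) | None stated | Yes |
| Protocol 10.5.1 | Consent to last follow-up visit | Yes |
| SAP 11.7.1 | Each trial group | Yes |

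On the second row, Protocol 7.2 and 7.3 use the term trial drugs in their headings. Section 7.2 starts with methotrexate in Arm A, and 7.3 lists methotrexate, hydroxychloroquine, sulfasalazine and folic acid beside Benepali. On that usage methotrexate is included. The term is not fully stable, because 10.4.2 defines a SUSAR by relation to the IMP and then restates it by relation to the trial drugs.

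The first sentence of 10.1 also conflicts with 10.5.1 in Arm C: events between consent and first dose are to be collected, yet they cannot occur during or after administration.

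Result: the texts conflict, but the operative recording and reporting rules cover all arms.

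**Step 2. Do the IMP-specific variables have the same safeguard?** In Protocol 4.4, the counts of patients with AEs and SAEs and the worsening of pre-existing conditions carry no IMP limit. Overdose, abuse and discontinuation do, and SAP 7.3 repeats that limit. No wider wording of these three safety variables appears elsewhere. Meanwhile the treatment withdrawal criteria in Protocol 6.4, which include laboratory limits, are not restricted by arm. The plan thus foresees toxicity-related stops in every arm.

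**Step 3. How many planned patients cannot contribute?** Arm sizes are those in Protocol 12.9 and SAP 9. The share with no IMP is (A + B) / (A + B + C).

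- Minimum: (44 + 16) / (44 + 16 + 16) = 60/76 = 78.9%.
- Maximum: (46 + 30) / (46 + 30 + 30) = 76/106 = 71.7%.

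The variables can be non-zero only among the 16 to 30 patients in Arm C, and there only for Benepali.

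**Step 4. Is AE-related discontinuation reported?** Neither Protocol 12.6 nor SAP 11.7.1 tabulates it, although both documents list it as a safety variable.

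**The case against.** The strongest reply is that the first sentence of 10.1 should not be read alone. The next sentence uses the wider term and disregards causality. Section 10.5.1 and the schedule have no arm restriction, and the bullet in 9.4.6 does not say that only IMP effects count. SAP 11.7.2 also summarises blood count, renal and liver tests by visit for each group, so laboratory signals are visible however an AE is defined. Drug stops are documented too: Protocol 7.3.3 requires CRF recording of stopping or switching on blood results, and SAP 8.1 lists a Changes in Medications CRF. Finally, with no discontinuation table planned, no planned B versus C result would be distorted.

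Most of this stands. A reader might infer that methotrexate harms fall outside the AE definition, that the AE count in Arms A and B would be zero whatever happened, or that the overall B versus C comparison is biased against etanercept. The documents do not support any of these. Each needs one sentence to override the rest of its own paragraph and 10.5.1, and nothing shows that recording followed that reading. Nor do the documents call methotrexate toxicity the main treatment harm.

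Two things survive. The IMP-only variables have no wider wording to rescue them. And the lack of a planned table does not cure a one-sided definition: the listed variable either goes unreported or, if reported as defined, can show events in one arm only. Raw records of methotrexate stops make the repair easy, but they do not place those stops in the defined variable.

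**Conclusion.** The point holds in two parts of unequal weight.

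- **AE definition:** an internal inconsistency that creates a risk of uneven recording. General AE and SAE counts are planned in all arms, and the documents give no basis for sizing any effect on them.
- **Overdose, abuse and AE-related discontinuation:** a definite defect of wording. These variables are empty by construction in 72% to 79% of planned patients, and AE-related stopping of methotrexate, hydroxychloroquine or sulfasalazine is counted by the discontinuation variable in no arm.

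The percentages assume the planned arm sizes and that no patient in Arm A or B receives Benepali. They give the share of patients whom the variables cannot reach; they do not estimate missed events or bias. Unequal measurement across arms is established only for these IMP-specific items.

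**What to change.** 1. Reconcile Protocol 10.1 and 9.4.6 with 10.5.1, so that an AE is any untoward occurrence from consent to the last follow-up visit, in any arm and whatever its relation to treatment.
2. In Protocol 4.4 and SAP 7.3, replace *an IMP* with *a study treatment* in the overdose, abuse and discontinuation items.
3. Add to SAP 11.7.1 a table of AE-related discontinuation by drug and arm, drawn from the AE, Changes in Medications and Concomitant Medications CRFs.
4. Leave the IMP-only wording for SUSAR reporting.

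If data collection is already complete, the SAP and trial report can still state which AE recording rule was applied, and the table can be built from the existing CRFs.

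The cost is wording, one more table and possibly higher reported counts in Arms A and B. No new data item is needed. The change concerns recording and reporting only and alters no dose or stopping rule.

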10.2 Defining serious adverse events (SAEs)

A **serious adverse event** (SAE) is an adverse event which is defined as serious, i.e. that it:

- Results in death. Death may occur as a result of the basic disease process. Nevertheless, all deaths occurring within 30 days of the last administration of the study agent must be treated as an SAE and reported as such. All deaths which may be considered as related to the trial agent, regardless of the interval, must be treated as a SAE and reported as such.
- Is life-threatening.
- Requires inpatient (overnight) hospitalization or prolongation of an existing hospitalization.
- Results in a persistent or significant disability or incapacity.
- Results in a congenital anomaly or birth defect.
- Additionally, important medical events that may not result in death, be life-threatening, or require hospitalization may be considered SAEs when, based on appropriate medical judgment, they may jeopardize the subject and may require medical or surgical intervention to prevent one of the outcomes listed in this definition.
- Any other significant clinical event, not falling into any of the criteria above, but which in the opinion of the Investigator requires reporting.

Other Reportable Information: Certain information, although not considered an SAE, must be recorded, reported, and followed up as indicated for an SAE. This includes the following:

- Pregnancy exposure to an IMP except for exposure to prenatal vitamins.
- Lactation exposure to an IMP, with or without an AE.
- Overdose of an IMP as specified in this protocol, with or without an AE. Baby formula overdoses without any AEs are excluded.
- Inadvertent or accidental exposure to an IMP, with or without an AE.
- Routine planned surgery

10.3. AEs of special interest

10.3.1. Pregnancy

Pregnancy is considered a form of SAE. If a pregnancy is confirmed, use of the IMP must be discontinued immediately. Both maternal and paternal exposures are considered other reportable information. For exposure involving the female partner of a male subject, the necessary information must be collected from the subject, while respecting the confidentiality of the partner. All pregnancies will be followed up until birth.

10.4. Exemptions from safety reporting

10.4.1. Efficacy endpoints and disease progression events

All events that are unequivocally due to progression of moderate to severe rheumatoid arthritis or lack of response should not be reported as an AE or SAE. This type of information will be captured in the study assessments.

Disease progression would include: increased joint pain, musculoskeletal pain, generalized body aches, uncontrolled RA, joint swelling, increased stiffness, limited motion, synoviorthesis (in or out of the hospital), and hospitalizations for RA-related procedures (joint replacement surgery, joint arthroscopy, synovectomy).

10.4.2. Defining suspected unexpected serious adverse reactions (SUSARs)

A **Suspected Unexpected Serious Adverse Reaction (SUSAR)** is a serious adverse event suspected to have a reasonable causal relationship to the investigational medicinal product where the nature or severity of the reaction is inconsistent with the available Reference

Safety Information, referring specifically to Section 4.8 'Undesirable effects' within the Summary Product Characteristics (SPC) for Benepali.

All SAEs assigned by the CI (or delegated clinician) as both suspected to be related to the trial drugs and unexpected are subject to expedited reporting.

10.5. Recording and reporting of AEs

10.5.1. Recording and reporting of all AEs

Determination of AEs should be based on the signs or symptoms detected during the physical examination and on clinical evaluation of the subject, and should be assessed and recorded at every visit. Signs and symptoms must be recorded using standard medical terminology. Subjects considered incapable of giving consent would not be considered for this study.

AEs and SAEs will be collected from the signing of the informed consent form until the last follow up visit. The Investigator must instruct the subject to report AEs and SAEs during this time period.

During the time period specified above, the Investigator will:

- Record all AEs and SAEs on source documents.
- Record all AEs and SAEs in the CRF for subjects who are not screen failures.

The Investigator must follow up on all AEs and SAEs until the events have subsided, returned to baseline, or, in case of permanent impairment, until the condition has stabilized, within the duration of the trial for each participant. There will be no follow up of AE's past the last follow up visit for each participant.

10.6. SAE and SUSAR reporting requirements

All SAEs assigned by the local Principal Investigator as both suspected to be related to protocol-treatment and unexpected will be reviewed by the Chief Investigator (CI). The CI, local PI or other medically qualified and delegated individual may declare an SAE a SUSAR.

All investigators should refer to the trial-specific Reference Safety Information when determining whether a SAE is expected [specifically Section 4.8 'Undesirable effects' within the Summary Product Characteristics (SPC) for Benepali].

All SAEs, other information reportable as SAEs and follow-up information must be reported to the Sponsor QA office within 24 hours of the research team becoming aware of them, by emailing a completed SAE form 'CTT21 Serious Adverse Event Report' to the email address ([contact]). The Sponsor will confirm that the email was received.

In parallel, the research team must also notify the study funder (Samsung Bioepis) within one business day from first awareness of the event.

Suspected adverse reactions that are both serious and unexpected are subject to expedited reporting to the REC and MHRA.

Identifiable patient data, other than linked anonymised data required by the SAE form, must not be included when reporting SAEs and SUSARs.

The Sponsor¹ then will inform the MHRA^{2,3} [via the MHRA eSUSAR web portal] and the Research Ethics Committee^{2,3} (REC) of SUSARs within the required expedited reporting timescales.

1. All SUSARs must be reported to the QA Sponsor office via ([contact]) within 24 hours of the event being reported to the CI (or their research team).
2. SUSARs must be reported to the REC / MHRA within 7 calendar days of the CI (or their research team) being informed of the event, if they result in Death or are deemed to be life-threatening. Follow-up information must be reported within 8 calendar days.
3. Any SUSARs not resulting in death or deemed to be life-threatening must be reported to the REC / MHRA within 15 Calendar days of the CI (or their research team) being informed of the event. Follow-up information must be reported within 8 calendar days.

SUSARs will be reported in accordance with the requirements and provisions of the applicable national laws. They will all be signed off by the Chief Investigator or, in their absence, by a delegated individual.

10.6.1. Urgent safety measures

If the research team becomes aware of information affecting the risk/benefit balance of the trial they may take immediate action to ensure patient safety. Urgent safety measures deemed necessary must be reported immediately by telephone to the MHRA (in conjunction with the Sponsor) and to the main REC for the trial, and must be followed within three days by notice in writing setting out the reasons for the urgent safety measures and the plan for further action. The REC co-ordinator will acknowledge within 30 days.

10.6.2. Serious breaches of protocol

A **serious breach** is a breach which is likely to effect to a significant degree either:

- The safety or physical or mental integrity of the subjects of the trial; or the scientific value of the trial.

Serious breaches of GCP, the trial protocol and the Clinical Trial Authorisation will be reported to the Sponsor QA office within 24 hours from the time the research team becomes aware of the incident.

